6.3 Medical History

A subject listing and summary table for medical history will be presented using the SAS.

The following information items are obtained from the eCRF:

- Medical history (*Medical History* eCRF panel).

The medical history summary should be presented by age group (see Section 5.12: Examination of Subgroups).

6.4 Prior and Concomitant Therapies and Medication

Subject listings will be presented for the following items using the SAS:

- Haemophilia A treatment history.
- Prior PEGylated medications.
- Prior and concomitant medications.
- Prior and concomitant non-drug therapies.

No summary tables are planned for presentation of prior and concomitant therapies and medication.

The following information items are obtained from the eCRF:

- Haemophilia A treatment history (Haemophilia A Treatment History eCRF panel).
- Prior PEGylated medication history (Prior Pegylated Medication History eCRF panel).
- Prior and Concomitant Medication and non-drug therapies (Concomitant Medications/Non-drug Therapies eCRF panel).
- Information on AEs and medical histories for which the medication or non-drug therapy has been given (Adverse Events and Medical History eCRF panels).

Prior and concomitant medications, haemophilia A treatment history and prior PEGylated medications are coded using the latest version of the World Health Organization-Drug Dictionary (WHO-DD), which is updated twice a year.

The following derivations will be made based of the eCRF reported results:

- Assignment to prior or concomitant:
 - A medication or non-drug therapy should be assigned as “Prior” if the medication or non-drug therapy stopped prior to first BAX 855 administration in the PROPEL study.
 - A medication or non-drug therapy should be assigned as “Concomitant” if the medication or non-drug therapy:
 - Started after first BAX 855 administration in the PROPEL study; or
 - Started before the first BAX 855 administration in the PROPEL study and ended after first BAX 855 administration in the PROPEL study.
 - A medication or non-drug therapy should be assigned as “Unknown” if missing dates do not allow for assignments based on above rules.
 - Based on the reason for medication or therapy, the actual AE or medical history term will be obtained by linking the information from the respective eCRF panels.

6.5 Extent of Exposure

Subject listings will be presented for the following items using the SAS:

- BAX 855 study infusions (including lots used and interruptions).
- Exposure to BAX 855 study infusions.
- Dose adjustment.
- Postoperative prophylaxis.

Summary tables for exposure to BAX 855 will be presented using the SAS, FAS and PPAS. Summaries will be presented by age group.

The following information items are obtained from the eCRF:

- Study infusion information (Study Infusion eCRF panels).
- Dose adjustment (Change of Dose eCRF panel).
- Postoperative prophylaxis (Postoperative Prophylaxis eCRF panel).
- Body Weight (Vital signs eCRF panels).

Due to the study having two sources of BAX 855 infusion information being captured (subject diaries via third party vendor ERT and the eCRF), the SAS[®] data tranfered to IQVIA Biostatistics contain duplicate records for the same infusion. When these records are exact duplicates (including dates and times), IQVIA Biostatistics are to handle these

duplicates as such within the Analysis Data model (ADaM) programming. Records that are not exact duplicates, will not be regarded as duplicate records by IQVIA Biostatistics and will be presented.

The following derivations will be made based of the eCRF reported results:

- Infusion duration should be determined as:

$$\text{Infusion duration} = (\text{Infusion Stop Time} - \text{Infusion Start Time})$$

- Body weight-adjusted dose (IU/kg) should be derived as the total units infused (IU) divided by the last available body weight (kg) prior to the infusion. See to Section 5.5: Handling of Missing, Unused, and Spurious Data for imputation rules to be implemented.
- The total number of infusions is determined as the total count of the number of infusions, regardless of date and time, the subject had. Number of infusions will be determined overall and by reason for infusion as well as by the treatment arm assigned to at the time of receiving the treatment.
- The number of EDs is determined as the number of unique calendar days on which a subject received study medication or part thereof. Multiple infusions on the same day will still be considered as one ED. EDs will be determined overall as well as for each reason a study medication administration is given.
- The observation period for efficacy (OPE) measured in days, in the study for subjects should be determined as provided in Section 5.5.1: Annualized Bleeding Rate.
- The OPE (weeks) should be determined from the OPE (days) as provided in Section 5.5.1: Annualized Bleeding Rate.
- The OPE (months) should be determined from the OPE (days) as provided in Section 5.5.1: Annualized Bleeding Rate.
- The OPE in (years) should be determined from the OPE (days) as provided in Section 5.5.1: Annualized Bleeding Rate.
- The average number of infusions per time period (weeks, months, years) should be determined as the total number of infusions during the full observation period, divided by the duration for the particular time period (weeks, months, years).
- Total dose (IU/kg or IU as applicable) should be determined as the sum of all doses, overall and by reasons for infusion, during the observation period in the current study.

- The average dose per time period (weeks, months, years) should be determined as the total dose (IU/kg or IU as applicable), the subject received during the observation period in the PROPEL study, divided by the duration for the particular time period (weeks, months, years).
- Average dose per bleed is determined as the sum of all doses (IU/kg or IU as applicable) given to treat bleeding episodes, divided by the number of bleeds observed for the particular subject in the current study.

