11. ASSESSMENT OF EFFICACY

11.1 Bleeding Assessment

Each individual bleed, spontaneous or traumatic, will be recorded in the subject's diary, and/or recorded in physician/nurse/clinic notes. A bleed is defined as subjective (e.g., pain consistent with a joint bleed) or objective evidence of bleeding which may or may not require treatment with FVIII. For further definitions of bleeds see Section 23. Bleeds occurring at the same anatomical location (e.g., right knee) with the same etiology (i.e., spontaneous vs. injury) within 72 h of onset of the first bleed will be considered a single bleed.³⁰ A new bleed is defined as a bleed occurring >72 hours after stopping treatment for the original bleed for which treatment was initiated and had an initial moderate to excellent response to treatment.³⁰ Bleeding occurring at multiple locations related to the same injury (e.g., knee and ankle bleeds following a fall) will be counted as a single bleeding episode.

The subject will also indicate in the diary on a preselected scale the type of activity within 8 hours prior to the bleeding episode.

For the primary assessment, the total bleed rate in the second 6-month study period will be calculated (i.e., after the 6-month visit to the Completion/Termination Visit). The secondary outcome measures, spontaneous and traumatic ABR, and spontaneous AJBR will also be calculated from the recorded bleeds.

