6.6 Measurements of Treatment Compliance

A subject listing (using the SAS) and summary tables (using the SAS, PPAS and PKAS) on compliance.

Treatment compliance will be derived using results and derivations obtained from study exposure as described in Section 6.5: Extent of Exposure.

Treatment compliance will be based on the following:

- Adherence to the study medication administration schedule; and
- Adherence to recommended prophylactic dosing plan.

An infusion will be considered in adherence to the study medication administration schedule if it does not deviate by more than ± 8 hours from the PK-guided assigned dosing frequency:

Based on the treatment regimen, time that a subject was not covered by BAX 855 prophylaxis, will be determined. The time in minutes that a subject was not covered by BAX 855 prophylaxis is calculated as the sum of all time periods exceeding the planned infusion interval after a prophylactic infusion.

Time not exposed (minutes) should be set to 0 if the above derivation results in number of days less than 0.

The percentage of time a subject was covered by BAX 855 prophylaxis, should be derived as follows:

$$\begin{aligned} & \textit{Time Covered by Prophylaxis (\%)} \\ &= \frac{\textit{OPE(Minutes)} - \textit{Total Time not Covered (Minutes)}}{\textit{OPE(Minutes)}} \times 100 \end{aligned}$$

An infusion is considered to be in adherence to the recommended prophylactic dose if the actual amount infused (IU/kg) is between 90% and 110% of the planned/assigned dose (IU/kg) to be infused. Infusions with actual amount infused not recorded in the eCRF, will be excluded from the compliance calculations.

The number and percentage of infusions in adherence to the recommended prophylactic dosing plan, will be determined for each subject using the overall number of infusions for that subject as denominator.

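### SAP 6.5 removes only exact duplicate infusion records, so discordant diary/eCRF pairs may be counted twice; average dose per bleed also includes untreated bleeds in its denominator

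*SAP*

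**What the plan says.** SAP 6.5 explains that infusions are captured both in the subject diary, through a vendor, and in the eCRF, and that the transferred data "contain duplicate records for the same infusion". The rule for removing them is narrow. It opens "When these records are exact duplicates (including dates and times), IQVIA Biostatistics are to handle these" and goes on to say that such records are treated as duplicates in programming. For everything else: "Records that are not exact duplicates, will not be regarded as duplicate records by IQVIA Biostatistics and will be presented". No time tolerance is given, and no order of preference between the two sources.

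The derivations that follow use whatever records remain. "The total number of infusions is determined as the total count of the number of infusions, regardless of date and time, the subject had". Total dose is the sum of all doses, and SAP 7.2.6 takes weight-adjusted consumption from this section. Exposure days are protected, because "Multiple infusions on the same day will still be considered as one ED".

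SAP 6.6 builds compliance on the same records: "An infusion will be considered in adherence to the study medication administration schedule if it does not deviate by more than ± 8 hours" from the assigned frequency.

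For average dose per bleed, SAP 6.5 takes the doses given to treat bleeds, "divided by the number of bleeds observed for the particular subject in the current study". Protocol 11.1 defines a bleed as evidence of bleeding "which may or may not require treatment with FVIII". SAP 7.1.2 defines separately when a bleed counts as treated with BAX 855 (at least one linked infusion) and lists untreated bleeds on their own.

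**The concern.** Two people recording one infusion, a subject in a diary and a site nurse in the eCRF, can easily differ by a few minutes or in another field. Under the written rule such a pair is two infusions with two doses. The SAP's revision history shows that records of one infusion did differ: it mentions an infusion entered both as prophylaxis and as incremental recovery (IR), with only the IR record kept. SAP 6.5 itself contains no rule for such cases.

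Weight-adjusted consumption is a secondary outcome on which the two regimens are to be compared. If double recording arises mainly at scheduled site visits, its number per subject is about the same in both arms but its share is larger in the arm with fewer infusions. Each false pair also creates an interval of minutes, which fails the ±8-hour schedule rule. It can also disturb SAP 6.6.1, which uses time since the last infusion to match alternating doses.

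In dose per bleed, the numerator covers treated bleeds only and the denominator covers all bleeds. SAP 7.1.2.2 may widen the mismatch. It adds bleeds reported after a subject has left the study, collects no treatment data for them, and treats them in analysis as if captured in the study.

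**Working it through.** The documents give no duplicate rate, no expected consumption and no untreated share, so there is no figure of the plan's own to reproduce. What follows shows how the rules behave under stated assumptions.

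**Duplicate infusions: inputs**
- Period: 364 days (SAP 7.1.2, full 12-month period).
- Nominal intervals: 3.5 days in the 1-3% arm and 2 days in the 10% arm (protocol 8.7.5). Individual intervals may differ.
- Prophylactic infusions N: 364/3.5 = 104 and 364/2 = 182; ratio 182/104 = 1.75; difference 78.
- Scheduled site infusions: Baseline, Weeks 4 and 8, Months 3, 4.5, 6, 9 and 12 = 8 (protocol 21.3). Five are IR visits (Baseline, Months 3, 6, 9, 12; protocol 12.2 and 21.4). Three are trough-only visits (Weeks 4 and 8, Month 4.5).
- k = discordant pairs per subject that survive to analysis. This is an assumption: 0 if reconciliation is complete, 3 if only the non-IR site infusions are affected, 8 if all site infusions are.

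Inflation = (N + k)/N. Loss of schedule adherence from 100% = k/(N + k), one failed interval per pair.

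| k | Twice weekly | Every other day | Ratio | Difference | Adherence loss (points) |
|---|---|---|---|---|---|
| 0 | 104 | 182 | 1.75 | 78 | 0 / 0 |
| 3 | 107 (+2.9%) | 185 (+1.6%) | 185/107 = 1.73 | 78 | 3/107 = 2.8 / 3/185 = 1.6 |
| 8 | 112 (+7.7%) | 190 (+4.4%) | 190/112 = 1.70 | 78 | 8/112 = 7.1 / 8/190 = 4.2 |

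If instead a fixed share f of infusions is duplicated in both arms, every count is multiplied by 1 + f and the ratio stays at 1.75.

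In IU/kg, k duplicates add k × d to consumption, where d is the dose per infusion in that arm. The between-arm difference then changes by k × (d in the 10% arm − d in the 1-3% arm). The documents do not give these doses, so the sign of that change is not known.

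**Dose per bleed**

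Let u be the share of a subject's bleeds that were not treated. Then

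SAP figure = dose per treated bleed × (1 − u).

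For assumed u of 10%, 20%, 30% and 50%, the SAP figure is 0.90, 0.80, 0.70 and 0.50 of the dose per treated bleed. As a worked case with an arbitrary dose, take 6 bleeds, 4 of them treated with one infusion of 30 IU/kg: 120/6 = 20 under the SAP, and 120/4 = 30 per treated bleed.

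Surviving duplicates among bleed-treatment infusions act the other way, giving (1 + f)(1 − u). At f = 5% and u = 20% this is 1.05 × 0.80 = 0.84. At f = 10% and u = 10% it is 1.10 × 0.90 = 0.99, so the two faults can hide each other.

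**The case against.** The strongest reply is that few or no discordant pairs may reach the analysis. SAP 5.2 requires vendor and eCRF data to be reconciled before the final analysis; reconciliation could align discordant entries, after which the exact-match rule would delete them. Protocol 10.5 says e-diary data reach the CRF by validated transfer, which should give exact copies. SAP 4.2 describes the Study Infusion panels as the diary feed plus missed and on-site infusions, which reads as complementary rather than parallel capture. The revision history suggests that prophylaxis/IR pairs are already reduced to one record.

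Much of this stands, and it is why no size can be claimed. It does not remove the gap. The reconciliation line is generic and does not say that near-matches are merged, SAP 6.5 is written for data that still hold duplicates, and the prophylaxis/IR handling appears only in the revision history.

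Three stronger readings are tempting but not supported:
- *That consumption is wrong, or its between-arm gap understated.* No rate is given. The infusion difference is 78 in every scenario, the ratio moves only if duplicates are equal in number rather than in share, and the IU/kg gap depends on doses not stated. Consumption is also summarised descriptively, without a test.
- *That the per-protocol set is damaged.* Time covered in SAP 6.6 adds up only periods longer than the planned interval, so an extra record minutes later has essentially no effect on it. A loss of 7.1 points from full adherence leaves 92.9%, well above the 75% mark in SAP 4.4, and a meeting decides exclusions.
- *That dose per bleed is an error.* It is a stated definition and not a listed outcome measure. It misleads only if read as dose per treated bleed, but nothing in SAP 6.5 warns against that reading.

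**Conclusion.** The concern holds as a gap in the rules, not as a demonstrated error in the results. As written, SAP 6.5 counts twice any diary/eCRF pair that is still discordant after reconciliation, and this passes into infusion number, weight-adjusted consumption and schedule adherence. The illustrative range is no effect if reconciliation is complete, +2.9% and +1.6% (twice weekly, every other day) if the three non-IR site infusions are double-recorded, and +7.7% and +4.4% if all eight are. These figures rest on nominal intervals, 364 days of prophylaxis and the same number of duplicates in each arm.

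Average dose per bleed is below dose per treated bleed by exactly the untreated share, apart from any duplicates in the numerator. That share is not in the documents. Whether bleeds reported after discontinuation enter the denominator is also unclear, and the SAP does not say what happens for subjects with no bleeds.

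The primary endpoint is a bleed outcome and is untouched. The point concerns descriptive secondary and exposure tables, and it is worth correcting because the correction is cheap.

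**What to change.** In SAP 6.5:
- Treat records as duplicates only when one comes from the diary and one from the eCRF, for the same subject, with the same units (and lot, where recorded) and start times within a short window stated in the SAP.
- Exempt perioperative and bleed-treatment infusions from automatic merging. A 60-minute window would not be safe for all infusions: protocol 22.3.2 samples at 15 ± 5 minutes after the loading dose and permits a supplemental loading dose.
- Do not merge on calendar day alone. Protocol 8.7.7 (Table 1) allows repeat bleed-treatment infusions every 8 to 12 or 12 to 24 hours, so true infusions could be lost. Send pairs with a missing time to listed manual review before database lock.
- Keep the eCRF record, move the prophylaxis/IR rule from the revision history into SAP 6.5, and list every removal.
- Report average dose per BAX 855-treated bleed, using the SAP 7.1.2 definition, in place of or beside dose per all bleeds with a clear label. State how subjects without a treated bleed and bleeds reported after discontinuation are handled.

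The cost is SAP wording, one programming step and some manual review. The downside is a small risk of merging two true infusions, limited by the cross-source condition and visible in the listing.

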6.6 Measurements of Treatment Compliance

A subject listing (using the SAS) and summary tables (using the SAS, PPAS and PKAS) on compliance.

Treatment compliance will be derived using results and derivations obtained from study exposure as described in Section 6.5: Extent of Exposure.

Treatment compliance will be based on the following:

- Adherence to the study medication administration schedule; and
- Adherence to recommended prophylactic dosing plan.

An infusion will be considered in adherence to the study medication administration schedule if it does not deviate by more than ± 8 hours from the PK-guided assigned dosing frequency:

Based on the treatment regimen, time that a subject was not covered by BAX 855 prophylaxis, will be determined. The time in minutes that a subject was not covered by BAX 855 prophylaxis is calculated as the sum of all time periods exceeding the planned infusion interval after a prophylactic infusion.

Time not exposed (minutes) should be set to 0 if the above derivation results in number of days less than 0.

The percentage of time a subject was covered by BAX 855 prophylaxis, should be derived as follows:

$$\begin{aligned} & \textit{Time Covered by Prophylaxis (\%)} \\ &= \frac{\textit{OPE(Minutes)} - \textit{Total Time not Covered (Minutes)}}{\textit{OPE(Minutes)}} \times 100 \end{aligned}$$

An infusion is considered to be in adherence to the recommended prophylactic dose if the actual amount infused (IU/kg) is between 90% and 110% of the planned/assigned dose (IU/kg) to be infused. Infusions with actual amount infused not recorded in the eCRF, will be excluded from the compliance calculations.

The number and percentage of infusions in adherence to the recommended prophylactic dosing plan, will be determined for each subject using the overall number of infusions for that subject as denominator.

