8.7.3 Description of Treatment

Subjects will be randomized to one of 2 PK-tailored prophylactic dose regimens (see Section 8.5) each of them targeting:

- FVIII trough levels of 1-3% with approximately twice weekly dosing, or
- FVIII trough levels of approximately 10% (8-12%) with dosing approximately every other day.

The individual subject's dose will be calculated by the sponsor and provided to the study site. Depending on subject's individual PK, different dosing intervals should be considered if single doses of >80 IU/kg are required or regular FVIII peak levels of 200% would be reached or exceeded.

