4.4 Per-Protocol Analysis Set (PPAS)

The Per Protocol Analysis Set (PPAS) is to comprise all subjects in the FAS who:

- Completed the second 6 months (ObsDay 183 to ObsDay 364) of prophylactic treatment. Defined as not having prematurely discontinued from the study.
- Had no major deviations from the protocol affecting the study results.

Major protocol deviations are defined in the Protocol Deviation Plan. Protocol deviations are obtained from the following sources:

- IQVIA Clinical Trial Management System (CTMS).
- Programmatic testing by IQVIA Biostatistics.
- The end of study, final Data review/analysis set assignment meeting.

During the course of the study, data review meetings (for data cleaning) will be held on a regular basis. During these meetings the quality of the data will be assessed.

Prior to performing any final analysis as set out in this Statistical Analysis Plan (SAP), a meeting will be held discussing the impact of any major protocol deviation on the analysis. If a subject presents with a major protocol deviation, it is not in itself cause to exclude the subject from the PPAS. Only at the protocol deviation discussion meeting will the decisions be made on whether a subject should be excluded from the PPAS or not, taking the major protocol deviation information into consideration. The meeting should be attended by participants from at least Biostatistics and Medical.

Below is a list of possible major deviations that may influence the study results, which will be discussed at the protocol deviation discussion meeting:

- Subjects less than 75% exposed to BAX 855 as derived in Section 6.6: Measurements of Treatment Compliance.
- Subjects less than 75% compliant to planned dosing regimen as discussed in Section 6.6: Measurements of Treatment Compliance.
- Use of expired or temperature compromised IP.
- Use of a Pegylated product other than BAX 855.

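### SAP 6.6 divides prophylactic dose adherence by all of a subject's infusions, so the compliance percentage falls as bleeding rises, and faster in the low-trough arm

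*SAP*

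**What the plan says.** SAP 6.6 bases compliance on the infusion schedule and on the prophylactic dose. The dose rule is: "An infusion is considered to be in adherence to the recommended prophylactic dose if the actual amount infused (IU/kg) is between 90% and 110" per cent of the planned or assigned dose. The number and percentage of adherent infusions are then found for each subject, "using the overall number of infusions for that subject as denominator". The only infusions that 6.6 removes are those with no recorded amount.

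SAP 6.6 takes its inputs from SAP 6.5, which defines the total as every infusion the subject had and adds: "Number of infusions will be determined overall and by reason for infusion". So the overall count covers all reasons together.

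SAP 4.4 uses the result in its list of possible major deviations: "Subjects less than 75% compliant to planned dosing regimen as discussed in Section 6.6: Measurements of Treatment Compliance". Time not covered by prophylaxis is a separate 75% item. On what follows from such a deviation, SAP 4.4 says "it is not in itself cause to exclude the subject from the PPAS", and "Only at the protocol deviation discussion meeting will the decisions be made on whether a subject should be excluded from the PPAS or not".

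SAP 6.6 plans compliance summary tables, and SAP 7.1.2 presents ABR comparisons on both the FAS and the PPAS.

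**The concern.** The numerator is judged against a prophylactic dose. The denominator also holds infusions that have no prophylactic dose to adhere to: bleed treatment, maintenance of haemostasis, perioperative dosing and the fixed-dose PK infusions. Each treated bleed can add to the denominator without adding to the numerator, so the measure of compliance depends on the trial's outcome.

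The dependence differs by arm. The low-trough arm has fewer planned infusions, so each extra one costs it more, and SAP 2.3 expects it to bleed more (40% bleed-free against 70%). Two things are at stake. The compliance summaries would show a gap between arms that is partly a product of the formula. And the list of subjects put forward for possible removal from the PPAS would depend partly on bleeding, in an open-label trial where the PPAS is used for ABR comparisons.

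**Working it through.** The 75% limit is stated without a derivation, so there is no plan figure to reproduce. The check is what the formula returns for a subject whose prophylactic dosing is known.

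**Inputs**
- Follow-up on the regimen: at least 52 weeks (Protocol 8.2), taken as 364 days.
- Low arm: "FVIII trough levels of 1-3% with approximately twice weekly dosing" (Protocol 8.7.3). At one infusion per 3.5 days, P = 364/3.5 = 104.
- High arm: about every other day (same section). P = 364/2 = 182.
- Infusions per bleed: 1 or 2 in 95.9% of bleeds in the pivotal study (Protocol 6.4.2). Two is used below, with 1 and 3 as a range.
- Assumption: every bleed infusion is additional to the schedule and scored as non-adherent.

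**Effect on the percentage.** With P correct prophylactic infusions and B bleed infusions, compliance = P/(P + B). At 2 infusions per bleed:

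| Bleeds per year | B | Low arm | High arm |
|---|---|---|---|
| 2 | 4 | 104/108 = 96.3% | 182/186 = 97.8% |
| 5 | 10 | 104/114 = 91.2% | 182/192 = 94.8% |
| 10 | 20 | 104/124 = 83.9% | 182/202 = 90.1% |
| 20 | 40 | 104/144 = 72.2% | 182/222 = 82.0% |

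The true dose adherence in every cell is 100%.

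**Distance to 75%.** If a share a of prophylactic doses is adherent, aP/(P + B) < 0.75 when B > P(a/0.75 − 1).
- a = 1.00: B > 34.7 (low) and B > 60.7 (high), so 35 against 61 infusions.
- a = 0.90: B > 20.8 and B > 36.4, so 21 against 37.
- a = 0.85: B > 13.9 and B > 24.3, so 14 against 25.

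At perfect adherence, 35 and 61 infusions correspond to 35 and 61 bleeds a year at 1 infusion each, 18 and 31 at 2, and 12 and 21 at 3.

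**How many fully adherent subjects would cross.** The documents give no bleed distribution for this population, so this is a range under an assumed negative binomial with 38–40% bleed-free over the year and 2 infusions per bleed. The share of low-arm subjects with at least 18 bleeds is about 0.3% at a mean ABR of 2, 2% at 3.04 (the paediatric study's mean, Protocol 6.4.2) and 8% at 5. With 58 subjects per arm (Protocol 8.1) that is 58 × 0.003 = 0.2, 58 × 0.02 = 1.2 and 58 × 0.08 = 4.6 subjects.

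**Surgery.** Protocol 22.4 describes dosing after major surgery as most commonly 2 infusions per 24 hours. Seven such days give 2 × 7 = 14 infusions, the low-arm limit at 85% adherence. SAP 5.3.2 leaves surgery periods out of efficacy, but SAP 6.6 does not leave these infusions out of compliance.

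**After the fix.** With prophylactic infusions only, the fully adherent subject scores 104/104 or 182/182 = 100%, whatever the number of bleeds.

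**The case against.** A reader might infer that compliant subjects who bleed will be dropped from the per-protocol set. The documents do not support that. A fully adherent low-arm subject needs about 18 to 35 bleeds a year at 1–2 infusions each to fall below 75%. Falling below only puts the subject on the agenda of a meeting, with Biostatistics and Medical present, that could see the reason for each infusion and keep the subject. This stands.

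Nor does a high bleeding rate at entry show that many would cross. Fourteen infusions, or 7 bleeds at 2 each, is the low-arm limit only if 15% of prophylactic doses are already off target, a rate the documents do not give. The strata of ABR 5 or more and on-demand treatment describe pre-study bleeding. On study everyone receives PK-guided prophylaxis, and the pivotal study's prophylaxis to on-demand ABR ratio was 0.10 (Protocol 6.4.2).

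The text can also be read more mildly. A bleed infusion has no assigned prophylactic dose, so the sponsor may intend to leave it out. If it is in, nothing bars one that happens to lie within 90–110% of the assigned dose from counting as adherent; Table 1 of the Protocol spans 10–60 IU/kg. If, say, half did so at 10 bleeds a year, the scores would be (104 + 10)/124 = 91.9% and (182 + 10)/202 = 95.0%, so the effect shrinks but remains. Finally, SAP 4.4 does not say which 6.6 measure its second 75% item uses. Dose adherence is the natural reading, because coverage has its own item and 6.6 defines no other percentage of infusions.

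These points limit the size of the problem. They do not make the denominator right, and the meeting would still start from flags that partly reflect bleeding.

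**Conclusion.** The denominator in SAP 6.6 does not match what the percentage is meant to measure. As written, compliance falls with bleeding even under perfect prophylactic dosing, and more in the low-trough arm: 91.2% against 94.8% at 5 bleeds a year and 83.9% against 90.1% at 10. The sure consequence is biased compliance summaries. The possible one is that a few frequent bleeders, or subjects with many surgical infusions, are flagged for PPAS discussion, earlier in the low arm (35 against 61 extra infusions at perfect adherence, 21 against 37 at 90%).

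A reader might also infer that the main result is at risk. It is not: SAP 7.1.2 counts bleeds in the primary analysis whatever the compliance. No distortion of the per-protocol bleed-free proportions has been shown.

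The figures assume exact 3.5-day and 2-day intervals over 364 days, with bleed infusions additional to the schedule and scored as non-adherent.

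**What to change.** In SAP 6.6, define the dose-adherence percentage with prophylactic infusions in both numerator and denominator. Count IR-visit infusions given at the assigned prophylactic dose as prophylactic, as SAP 5.4.1 already does when it defines the observation period. Exclude infusions for bleeds, maintenance of haemostasis, surgery and PK assessment from both. In SAP 4.4, state that the 75% item on the dosing regimen refers to this figure.

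The cost is about one sentence in 6.6 and a cross-reference in 4.4. SAP 6.5 already counts infusions by reason, so no new data are needed. If prophylactic infusions alone were always intended, the same sentence records that.

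The change should be in place before the protocol deviation meeting reviews any subject against the 75% item.
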